We conducted an extensive literature search and could find no published data on the effects of 250mg of armodafinil in treating fatigue in brain tumor patients. Given the trend toward positivity of the studies ongoing with 150 mg dose (77,78) further investigation is needed to decipher if further benefit from a higher dose is plausible. The 250 mg dose of armodafinil has been proven safe and efficacious in a study that showed positive results in patients with narcolepsy (109). In addition, there are ongoing trials listed on clinicaltrials.gov using 250mg of armodafinil in patients with results pending. Our proposed three-arm study complements both of those trials and other ongoing studies (110) by evaluating armodafinil in a more homogeneous population, specifically high grade glioma, and evaluating armodafinil for its effects on severe fatigue once radiation therapy has been completed. Given that fatigue is prevalent at the completion of radiation therapy, this seems the best endpoint to evaluate. Cognitive difficulties are one of the elements of fatigue and hence, these two problems are sometimes difficult to tease apart. Fatigue measurement is more advanced than cognitive measurement, due to problems with practice effects for neuropsychiatric measures and the lack of understanding of how fatigue, sleep and mood impact cognition. Therefore, we believe that evaluating fatigue as the primary endpoint and cognition as a secondary endpoint is well justified.

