#### 2.2 Secondary

- 2.2.1 To evaluate the tolerability at 8 weeks of 150mg and 250mg armodafinil in this patient population**
- 2.2.2 To assess the effect of armodafinil at 8 weeks on cognitive function in patients with high grade glioma.**
- 2.2.3 To assess the impact of armodafinil on global quality of life and other fatigue endpoints in this patient population with high grade glioma.**
- 2.2.4 Explore the correlation between the BFI, PROMIS, and PRO-CTCAE measures, as well as, the relationship of fatigue and cognitive difficulties.**

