#### **4.1.2 Neurocognitive Tests Format**

The credentialed site study team member will administer the neurocognitive tests to the patient using the patient questionnaire titled "Neurocognitive Examiners Booklet". On follow-up visits, it is preferred that patients complete the neurocognitive test battery **before** seeing the physician since the emotional impact of the results of their follow-up brain scan may influence the patient's performance on the neurocognitive assessments. The questionnaire booklet will take approximately 15 minutes to complete and includes the following tests:

- a) Symbol Digit Modalities Test (Smith, 1982).
- b) Controlled Oral Word Association.
- c) Trail Making Test A and B (Reitan 1958).

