## **11.2 Objective Cognitive Measures (Primary Cognitive Endpoint)**

The neuropsychological battery proposed for this study overlaps with batteries used in numerous North Central Cancer Treatment Group (NCCTG) multi-center trials for studies in patients with CNS tumors without any problems or complications.

Clinicians and researchers must balance the often conflicting goals of obtaining valid PRO data while not burdening patients or interfering with the provision of care in a busy clinical setting. When surveyed about the preferred properties for an assessment battery for neurological and behavioral function, 191 experts in clinical and epidemiologic research reported it should be brief, precise, and easy to administer, score, and interpret (93).

The Symbol Digit Modalities Test (SDMT; Smith, 1982) is a measure of attention, visual tracking, and psychomotor speed. The task consists of a brief practice, followed by a 90-second test trial. Subjects are given a key in which 9 symbols are paired with each of the digits 1 through 9. Below the key is a grid in which a random series of the symbols appear above empty boxes. The task is to fill in the correct digit under each symbol, without skipping boxes, as quickly as possible for 90 seconds. This task has been found to be a particularly sensitive indicator of brain dysfunction (95).

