### **11.2.2 Trail Making Test**

Trail Making is a two-part sequencing task which requires subjects to connect numbered dots in order (Part A) and then to connect dots alternating between numbers and letters (Part B). Score is time of completion, with each trial scored separately. Part A measures psychomotor speed, concentration, and visual scanning. Part B requires the cognitive functions required for Part A, with added recruitment of cognitive flexibility (executive function) (86). This test has a long history of use in clinical neuropsychology, and has been found to be very sensitive to brain dysfunction in general (96, 97).

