## 16.4 Secondary Endpoints

**16.4.1 Other time points:** The same analyses carried out using the 8 week assessment data will be used for analysis of data from the other time point assessments.

**16.4.2 Other fatigue measures:** The other fatigue items ("usual", "usual" and "now") as well as the impact of fatigue items from the BFI, the PRO-CTCAE, and the summated score from the PROMIS fatigue measure will be analyzed separately in turn comparing the average of these variables for each treatment using Kruskal-Wallis testing for change from baseline to four weeks, AUC over the entire treatment period, and repeated measures ANOVA using all treatments and all time points.

**16.4.3 Cognitive function:** The same analyses outlined for the other fatigue measures will be carried out for each of the cognitive function tests.

**16.4.4 Quality of life:** The same analytical approaches will be used to compare the three treatments in terms of QOL as was outlined for the other fatigue measures.

**16.4.5 Safety and tolerability of armodafinil:** Comparison of the proportion of patients reporting adverse events via the CTCAE items will be compared across treatment arms using a Fisher's exact test.

**16.4.6 Area under the curve (AUC) and summary statistics:** For the continuous measures mentioned above, AUC summary statistics will be generated for each patient to represent the overall experience reported by patients for each endpoint (e.g. fatigue) by combining the data from baseline, weeks 4, and 8 assessment points. The average of these AUC variables will be compared between the two treatment arms using two-sample t-tests. Further summary statistics will be constructed for the categorical variables to indicate whether the patient ever responded over the entire treatment period. These categorical variables will be compared between treatment groups via Fisher's exact tests.

**16.4.7 Repeated measures analysis:** The overall experimental layout will be examined via the construction of a repeated measures model using data from all assessment time points involving the continuous variables described above. Tests for time by treatment interaction will be carried out by the profile analysis methods of Srivastava. Covariates such as age, gender and other clinical variables may be included to test their impact on the initial efficacy tests of the primary and secondary analyses described above. Use of the Optune® device will also be included as a descriptive factor.

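### The cognitive goal is set at week 8, but section 16.4.3 plans no direct week-8 comparison and names no deciding result among four test scores and three methods

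*Combined protocol and SAP*

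**What the plan says.** - **Goal.** Section 2.2.2: "To assess the effect of armodafinil at 8 weeks on cognitive function in patients with high grade glioma".
- **Rank.** The heading of section 11.2 reads "Objective Cognitive Measures (Primary Cognitive Endpoint"; FACT-Cog in 11.1.5 is headed as the secondary cognitive endpoint. Within the trial as a whole, section 1.4 holds that "evaluating fatigue as the primary endpoint and cognition as a secondary endpoint is well justified".
- **Scores.** Section 4.1.2 lists the "Symbol Digit Modalities Test (Smith, 1982", "Controlled Oral Word Association", and Trail Making A and B. For the trails, 11.2.2 says "Score is time of completion, with each trial scored separately". That makes four scores.
- **Analysis.** Section 16.4.3: "The same analyses outlined for the other fatigue measures will be carried out for each of the cognitive function tests". The analyses it points to, in 16.4.2, are "using Kruskal-Wallis testing for change from baseline to four weeks, AUC over the entire treatment period, and repeated measures ANOVA".
- **Detail.** Section 16.4.6 compares AUC by two-sample t-tests and speaks of two arms, although the trial has three. Section 16.4.7 tests time by treatment.
- **Multiplicity.** Sections 16.1 and 16.2 decline adjustment, with a reason that concerns the two dose-placebo comparisons. Nothing is said about several cognitive scores or methods.

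**The concern.** The plan ranks objective cognition above self-report and fixes the time point of the goal, and then specifies analyses that use neither decision. The only change-score analysis stops at week 4. AUC and repeated measures include week-8 data but do not estimate the week-8 difference. With four scores, several methods and no stated order, a reader of the results cannot tell which p-value answers goal 2.2.2. If one of them falls below 0.05, the plan gives no basis for believing or dismissing it, and the trial is meant to inform what goes into phase III.

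**Working it through.** **1. Does any planned analysis answer the week-8 question?**

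| Analysis | Visits used | What it tests |
|---|---|---|
| Kruskal-Wallis on change | baseline, week 4 | three-arm difference in change at week 4; no week-8 data |
| AUC | baseline, weeks 4 and 8 | average level; by the trapezium rule with equal spacing the weights are 1/4, 1/2, 1/4, so week 8 counts for a quarter |
| Repeated measures | baseline, weeks 4 and 8 | whether the arm profiles are parallel |

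Section 16.4.1 does not fill the gap. It extends the week-8 analyses to other time points and does not add a week-8 change analysis to 16.4.2.

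**2. Chance of at least one nominal p<0.05 with no effect**

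The plan states no error rate or power for cognition, so there is no figure to reproduce. The input of 100 per arm comes from 16.2. The uncorrected two-proportion formula for 10% against 25% gives [1.96√(2×0.175×0.825) + 0.842√(0.09+0.1875)]²/0.15² = 99.5, so 100 per arm, with 80.2% power. (Exact enumeration of the Fisher test named there gives 76.2%; that does not bear on this point.)

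*Counting.*
- 4 scores × 3 methods = 12 tests.
- With the AUC t-test run for each dose, 4 × (1+2+1) = 16.
- If a reader adds the missing week-8 Kruskal-Wallis, 4 × 5 = 20.
- If the tests were independent, 12 of them would give 1 − 0.95¹² = 46.0%.

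The tests are correlated, so the rate was simulated: three arms of 100, four scores, three visits, multivariate normal, 3,000-5,000 replicates, each test at two-sided 0.05. *Assumed, because the documents do not give them:* between-test correlation 0.3-0.7 and between-visit correlation 0.5-0.85. Results at between-visit correlation 0.7:

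| Reading | r = 0.3 | r = 0.5 | r = 0.7 |
|---|---|---|---|
| 12 tests (three-arm, with time by treatment) | 39% | 37% | 31% |
| 16 tests (AUC t-test for each dose) | 48% | 44% | 39% |
| 20 tests (plus week-8 Kruskal-Wallis) | 53% | 49% | 44% |

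Replacing time by treatment with the overall treatment effect in the 12-test reading gives 28-36%. Over all readings the range is about 28-53%. A single Kruskal-Wallis test on one score simulated at 4.7-5.5%.

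**3. What the week-8 baseline-adjusted comparison gains**

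Take one score, one dose against placebo, 100 per arm, a shift of 0.3 SD at weeks 4 and 8, and visit correlation 0.7 (both assumed). Power = Φ(δ√50/σ − 1.96).
- ANCOVA: σ² = 1 − 0.7² = 0.51; 0.3×7.071/0.714 = 2.97; power 84%.
- Change score: σ² = 2(1 − 0.7) = 0.60; 0.3×7.071/0.775 = 2.74; power 78%.
- Raw AUC: shift 0.75×0.3 = 0.225; σ² = 0.375 + 0.7×0.625 = 0.8125; 0.225×7.071/0.901 = 1.77; power 42%.

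**4. Is a composite needed?**

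For a mean of four z-scores the gain over one score is √(4/(1+3r)) = 1.45, 1.26, 1.14 at r = 0.3, 0.5, 0.7 when all four shift equally. Shifts below are in SDs of the variable compared, without credit for baseline adjustment.

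| True effect | Composite | One responding score alone | Any of four, Bonferroni 0.0125 |
|---|---|---|---|
| All four shift 0.3 SD | 87 / 77 / 67% | 56-57% | 73 / 66 / 58% |
| Two shift 0.4 SD | 54 / 43 / 36% | 81% | 83 / 80 / 76% |
| One shifts 0.4 SD | 18 / 15 / 13% | 81% | 64% |

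(Triplets are for r = 0.3 / 0.5 / 0.7.) A composite still run through all three methods keeps an error rate of about 13-17%, so it does not by itself produce one answer.

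**The case against.** Cognition is a secondary endpoint in a trial of preliminary efficacy. The label in 11.2 only ranks objective tests above FACT-Cog. No stopping rule or sample-size statement uses cognition, and the plan openly prefers not to adjust. All of that stands, and it limits the consequence. A reader might infer that the trial has up to an even chance of a false conclusion; the documents do not support this, because the trial's conclusion rests on the fatigue response at 8 weeks. The stated reason for not adjusting does not, however, reach four scores by three methods, and no ranking explains why a week-8 goal lacks a week-8 comparison.

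A reader might also infer that the plan should be replaced by a composite because a composite has more power. That too is unsupported. The gain is over a single test, when the effect is shared. Taking any unadjusted significant score as success has 78-90% power when all four shift by 0.3 SD, at least as much as the composite, though without error control. Sections 11.2 to 11.2.2 give the tests a common element of speed but also distinct ones: visual tracking, verbal fluency and cognitive flexibility. An effect confined to one or two tests is therefore possible, and the composite would largely miss it.

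Finally, two doses against placebo still give two p-values, with about a 9% chance of at least one below 0.05. That is consistent with the stance declared in 16.1.

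**Conclusion.** The gap is real and can be read directly from the text: the goal is at 8 weeks, the named change analysis is to 4 weeks, and nothing is marked as deciding. That part rests on no assumption. The size of the multiplicity, roughly 28-53%, rests on assumed correlations, on 100 evaluable patients per arm, on a 5% two-sided level that the plan states only for the primary endpoint, and on how 16.4.2 and 16.4.6 are read. The upper end includes a week-8 test that the plan does not name. It is the chance of some nominal p<0.05 among secondary cognitive results. The week-8 ANCOVA is justified on its own, since it answers the goal and is more efficient than the planned methods under the assumptions shown. The choice between a lead test, Holm and a composite is a trade-off that the sponsor should make in advance. The point should be corrected before unblinding; it does not affect the primary endpoint.

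**What to change.** In 16.4.3:
1. State that the deciding cognitive analysis is the week-8 comparison of each dose with placebo by ANCOVA, adjusted for the baseline score of the same measure. Keep the two dose contrasts unadjusted, as in 16.1, and say so.
2. Apply it to one prespecified cognitive result, chosen from: (a) one lead test; (b) the four tests with Holm adjustment within each dose comparison; (c) a mean z-score with direction, scaling and handling of a missing component defined.
3. If Trail Making enters the deciding result in any form, give a rule for tests stopped at 3 minutes (Part A) or 5 minutes (Part B) under Appendix VIII. These patients have no completion time, and 16.8 has no rule for them.
4. Label the week-4, AUC and repeated-measures results supportive.

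Cost: about one paragraph. No new data are needed, since section 4.0 already schedules the tests at baseline and weeks 4 and 8. Option (a) without Trail Making is the simplest. Options (b) and (c) need the rule for stopped tests. Option (c) also needs the scoring definition, and the sponsor accepts the loss of power if only one or two tests respond.

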## **8.0 DOSAGE MODIFICATION BASED ON ADVERSE EVENTS**

The study medication dose should be stopped for any grade 3 or worse toxicities related to study agent, or at the patient's discretion regarding toxicity. Any of the above should be clearly recorded on the Adverse Event Form.

Patients can be discontinued abruptly (no need to taper).

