## 10.2 CTCAE Routine Study Reporting Requirements

### \* Combinations of CTCAE Grade & Attribution Required for Routine AE Data Submission on Case Report Forms (CRFs)

Attribution	Grade 1	Grade 2	Grade 3	Grade 4	Grade 5
Unrelated			a	a	a
Unlikely			a	a	a
Possible		a	a, b	a, b	a, b
Probable		a	a, b	a, b	a, b
Definite		a	a, b	a, b	a, b

- a) Adverse Events: Other CRF - Applies to AEs occurring between registration and within 30 days of the patient's last treatment date, or as part of the Clinical Follow-Up Phase.
- b) Adverse Events: Late CRF - Applies to AEs occurring greater than 30 days after the patient's last treatment date.

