## 13.0 TREATMENT/FOLLOW-UP DECISION AT EVALUATION OF PATIENT

If the patient discontinues the study agent prior to 8 weeks, the patient will go off study.

A patient is deemed *ineligible* if after registration, it is determined that at the time of registration, the patient did not satisfy each and every eligibility criteria for study entry. If the patient received treatment, all data up until the point of confirmation of ineligibility must be submitted. If the patient never received treatment, on-study material must be submitted.

A patient is deemed a *major violation*, if protocol requirements regarding treatment in cycle 1 of the initial therapy are severely violated that evaluability for primary end point is questionable. All data up until the point of confirmation of a major violation must be submitted.

A patient is deemed a *cancel* if he/she is removed from the study for any reason before any study treatment is given. On-study material and the End of Active Treatment/Cancel Notification Form must be submitted. No further data submission is necessary.

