**15.1.7 Known potential toxicities**

The use of armodafinil is contraindicated in patients with hypersensitivity to armodafinil, modafinil, or any component of the formulation.

Use is not recommended in patients with a history of angina, cardiac ischemia, recent history of MI, left ventricular hypertrophy, or patients with mitral valve prolapse, who have developed mitral valve prolapse syndrome with previous CNS stimulant use.

Angioedema and hypersensitivity (with rash, dysphagia, and bronchospasm) have been observed with armodafinil. Small average increases in mean systolic and diastolic blood pressure were seen in patients with narcolepsy taking armodafinil when compared to placebo.

Serious and life-threatening rashes including Stevens-Johnson syndrome, toxic epidermal necrolysis, and drug rash with eosinophilia and systemic symptoms have been reported with modafinil, the racemate of armodafinil. Most cases have been reported within the first 5 weeks of therapy.

In pre-approval narcolepsy, OSA and SWD controlled trials of armodafinil, anxiety, agitation, nervousness, irritability, and depression were reasons for treatment

discontinuation more often than for placebo. Cases of suicide ideation were also observed in clinical trials.

The use of armodafinil may impair the ability to engage in potentially hazardous activities.

The agent should be administered at a reduced dose for patients with severe hepatic impairment. There is inadequate information to determine the safety and efficacy of dosing patients with severe renal impairment. Elimination of the agent and its metabolites may be reduced in elderly patients. Consideration should be given to the use of lower doses in this population.

Headaches are dose related and reported in > 10% of patients. Adverse reactions reported in 4 to 10% of patients include nausea (dose related), dizziness, insomnia (dose related), anxiety, and diarrhea. Adverse events reported in < 4% of patients include: depression (dose related), dyspepsia, fatigue, palpitations, rash (dose related), upper abdominal pain, agitation, anorexia, constipation, contact dermatitis, decreased appetite, depressed mood, attention disturbance, dyspnea hyperhidrosis, increased heart rate, flu-like syndrome, loose stools, migraine, nervousness, pain, paresthesia, polyuria, pyrexia, thirst, tremor, xerostomia (dose related), and vomiting.

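### Tolerability (goal 2.2.1) is compared only through the proportion of patients with an adverse event, which dilutes intolerance; stopping the drug, its most direct sign, is not compared between arms

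*Combined protocol and SAP*

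**What the plan says.** Section 2.2.1 sets the goal: "To evaluate the tolerability at 8 weeks of 150mg and 250mg armodafinil in this patient population".

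Section 16.4.5 gives the only analysis for it: "Comparison of the proportion of patients reporting adverse events via the CTCAE items will be compared across treatment arms", by Fisher's exact test. It states no grade cut-off, time window or denominator. No other part of 16.4 compares discontinuation, time on drug or exposure. Section 16.6 looks at grade 4 or higher events by arm, but only as a rule for suspending accrual.

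Section 8.0 has no dose-reduction step. The drug "should be stopped for any grade 3 or worse toxicities related to study agent", "or at the patient's discretion regarding toxicity". Section 13.0 adds: "If the patient discontinues the study agent prior to 8 weeks, the patient will go off study".

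On what is recorded:
- Section 8.0, about both kinds of toxicity stop: "Any of the above should be clearly recorded on the Adverse Event Form".
- Section 10.2, about the routine adverse-event form: "Applies to AEs occurring between registration and within 30 days of the" last treatment date. Its table requires grade 2 events if at least possibly related and grade 3 or higher whatever the attribution. It does not require grade 1 events.
- Section 10.6 lists one event, headache, for grading at every evaluation.
- Section 4.0 schedules adverse-event assessment at baseline, week 4 and week 8. The phone contacts in Appendix XII are also at weeks 4 and 8.

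Section 15.1.7 reports that in earlier armodafinil trials "anxiety, agitation, nervousness, irritability, and depression were reasons for treatment" discontinuation more often than with placebo. It gives no rate.

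**The concern.** With fixed doses and no reduction step, stopping the drug is the most direct sign that a patient could not tolerate it. The protocol's own drug information points to discontinuation as a known difference from placebo. The planned comparison does not isolate it, for two reasons.

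First, the measure is blunt. A patient with a related grade 2 event who takes all 56 tablets counts the same as one who stops in week 2. Grade 3 or higher events are collected whatever their cause, and 16.4.5 does not restrict the count to related events. In high-grade glioma, events of the disease and of concurrent chemotherapy may therefore add a background common to all arms.

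Second, capture of mild stops is fragile. A patient who stops by choice for grade 1 nervousness is outside the Section 10.2 table and reaches the adverse-event data only through the recording sentence in 8.0. Having gone off study, that patient also loses the later scheduled assessments.

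At stake is whether the trial can answer a goal that it sets for both doses.

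**Working it through.** The plan states no rate, power or sample size for tolerability, so there is no figure to reproduce. The only input from the plan is 100 evaluable patients per arm (Section 16.2). All rates below are assumptions.

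**Set-up.** Let q be the share of an arm that stops for toxicity, r the share of the remaining patients with a recorded event (taken as equal in both arms), and c the share of toxicity stops recorded as an event. The ever-reported proportion is

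P = c·q + (1 − q)·r.

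Take q = 5% in one arm and 20% in the other. Power is from exact enumeration of Fisher's test, two-sided 5%, 100 per arm.

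**Full recording (c = 1), r = 20%.**
- Arm 1: 0.05 + 0.95 × 0.20 = 0.24.
- Arm 2: 0.20 + 0.80 × 0.20 = 0.36.
- The 15-point difference in stops becomes 12 points. In general it is multiplied by (c − r), here 0.8.
- Power for 24% against 36%: 40%.
- Power for the stops themselves, 5% against 20%: 88%.

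**Effect of the background rate and of capture.**

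| Recorded share c | Background r | Event proportions | Power |
|---|---|---|---|
| 1 | 20% | 24% vs 36% | 40% |
| 1 | 40% | 43% vs 52% | 22% |
| 1 | 60% | 62% vs 68% | 11% |
| 0.5 | 20% | 21.5% vs 26% | 9% |

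In the last row the proportions are 0.5 × 0.05 + 0.95 × 0.20 = 0.215 and 0.5 × 0.20 + 0.80 × 0.20 = 0.26.

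**Smaller differences in stopping.** Comparing discontinuation directly has 59% power for 5% against 15%, and 44% for 10% against 20%. It is the sharper measure, but it is not well powered for every plausible difference. An estimate with a confidence interval is therefore more useful than a test alone.

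**Direction.** P rises with q whenever c > r. The ever-reported proportion thus ranks the arms correctly as long as the recording rate for toxicity stops exceeds the background event rate.

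**The case against.** The strongest reply is that the protocol already catches these patients. Section 8.0 requires toxicity stops to be recorded, with no lower grade limit for stops by patient choice. Section 10.2 keeps the routine reporting window open to 30 days after the last treatment. Headache is graded at each evaluation, and the phone guide asks staff to document any side effect that is reported. A by-arm table of stops could be produced from the existing forms in any case.

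Most of this stands, and it limits the point. A reader might infer that early stoppers cease to contribute adverse-event reports, so that the less tolerable dose looks better. The documents do not support that. With the 8.0 recording and the 10.2 window, a patient who stops for toxicity normally enters the numerator, and an ever-reported count ranks the arms correctly unless c falls below r. A reversal could also arise if only week-8 reports were counted and stoppers were entered as having none. Section 16.4.5 does not state that rule. Its silence is a reason to define the window, not evidence that the plan ranks the doses wrongly.

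A reader might also infer that the choice between 150 mg and 250 mg rests on this comparison. No section says so: 16.1 speaks of promising information in general, and the rule in 16.7.1 for closing the 250 mg arm uses effect size.

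The event proportion can also perform well when the drug raises tolerated events too. Suppose 25% on placebo have an event, 20% of the 250 mg arm stop with every stop recorded, and 40% of the others in that arm have an event. The 250 mg proportion is 0.20 × 1 + 0.80 × 0.40 = 52%, and power is 97%. But that result would show that events are more frequent, without separating events that patients tolerate from those that make them stop.

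The reply does not meet the narrower point: even with perfect recording, the planned measure dilutes stopping, and no comparison of stopping is specified.

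**Conclusion.** The point holds as one about dilution and an unnamed endpoint. The any-event proportion is a legitimate safety summary but a weak measure of goal 2.2.1. In the illustration its power is 40%, against 88% for comparing stops directly, and it falls to 11% as the background event rate rises to 60%. If only half of toxicity stops are recorded, it is 9% at a 20% background. These figures rest on assumed stop rates of 5% and 20%, a background rate equal in both arms, and 100 patients per arm. The documents supply only the last.

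The point does not extend to a claim that the plan favours the less tolerable dose, or that stoppers vanish from adverse-event reporting. The primary endpoint analysis is not part of this point. It should be fixed, because the better measure is available from data already collected.

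**What to change.** 1. In Section 16.4.5, name as a tolerability endpoint the proportion of treated patients who stop study drug before week 8 for an adverse event, or by their own choice because of toxicity, at any grade. Report all-cause discontinuation beside it. Compare each dose with placebo and 250 mg with 150 mg, giving the difference with a 95% confidence interval. The sources are the End of Active Treatment/Cancel Notification Form and the Adverse Event Form, both already in the Section 18.2 schedule.
2. Define the adverse-event proportion: any event of a stated grade, from first dose to 30 days after last dose, among all treated patients.
3. Reconcile Sections 8.0, 10.2 and 13.0 on what is collected after an early stop, including whether a grade 1 event that led to a stop is entered although the 10.2 table does not require grade 1 events.

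The cost is a wording change and a small amount of extra secondary analysis. No added patients or visits are needed.
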